1. INTRODUCTION

Lung cancer is the most fatal malignancy in China, as estimated by National Cancer Center of China,¹ accounting for 828,100 new cases, and 657,000 deaths in 2016. Non-small cell lung cancer (NSCLC), constituting 80%-85% of lung cancer, is most often diagnosed in advanced stages, where surgery and local radiotherapy are no longer curative or indicated.² Since the first anaplastic lymphoma kinase (ALK) tyrosine kinase inhibitors (TKI) approved in United States in 2011 and 2013 in China, the response and overall survival of ALK-positive NSCLC patients were significantly improved as compared with empiric chemotherapy.³ Subsequently, more second-generation ALK TKIs emerged, including alectinib, brigatinib, ceritinib and ensartinib,⁴⁻⁸ with notably longer median progression free survival (mPFS) and higher intracranial response rate. However, drug resistance yet develops inevitably, mostly due to ALK resistant mutation (e.g., I1171N, L1196M and G1202R),^{9,10} and intracranial progression, a major cause of illness and death.¹¹⁻¹⁵

Lorlatinib (Pfizer) is a novel third-generation ALK TKI that is more potent than second-generation ALK TKIs in biochemical and cellular assays and has the broadest coverage of ALK resistance mutations that have been identified.^{9,16,17} Lorlatinib was designed to cross the blood–brain barrier in order to achieve high exposures in the central nervous system (CNS).^{18,19} In phase 1 and 2 studies, lorlatinib had potent antitumor activity after the failure of previous ALK TKIs (first-generation, second-generation, or both).^{19,20} In particular, lorlatinib had marked intracranial activity in previously treated patients with baseline CNS disease, including leptomeningeal disease.^{11,12,20} In an ongoing China only phase 2 study, lorlatinib exhibited highly consistent antitumor activity, intracranial efficacy and safety profile as global phase 2 study in patients with progression on ALK TKIs,²¹ reconfirming superior efficacy of lorlatinib in combating ALK resistance.

The CROWN trial is a global, randomized, phase 3 trial comparing lorlatinib (n=149) with crizotinib (n=147; the standard-of-care first-line treatment at the time of trial

initiation) in patients with previously untreated advanced ALK-positive NSCLC.²² At the time of first data cutoff, the mPFS was not reached (NR; 95% confidence interval [CI], NR=NR) in the lorlatinib group, as compared with 9.3 months (95% CI, 7.6-11.1) in the crizotinib group by BICR. The percentage of patients who were alive without disease progression at 12 months was 78% in the lorlatinib group and 39% in the crizotinib group (hazard ratio, 0.28, 95% CI, 0.19-0.41); $P < 0.001$, one-sided). The hazard ratio favored lorlatinib over crizotinib across all prespecified patient subgroups defined according to baseline characteristics and stratification factors. At the second data cutoff, the mPFS was yet NR (95% CI, NR-NR) in the lorlatinib group, as compared with 9.3 months (95% CI, 7.6-11.1 months) in the crizotinib group by BICR.²² 24-month and 36-month PFS rate were distinctly higher in the lorlatinib group of 68.2% and 63.5%, as compared with 21.5% and 18.9% in the crizotinib group (hazard ratio, 0.27, 95% CI, 0.184-0.388). For patients with measurable brain metastases at baseline, lorlatinib achieved 72% intracranial complete response (CR) rate, and 83% intracranial objective response rate (ORR). Time to intracranial progression by BICR was remarkably longer with lorlatinib than crizotinib in the intention-to-treat population as well as in patients with and without baseline brain metastases, in which 8 out of 37 patients with baseline brain metastases and only 1 out of 112 patients without baseline brain metastases had intracranial progression after median follow-up over 36 months. This indicates that lorlatinib possesses the potential to clear existing brain metastases, meanwhile prevents new metastatic lesions in the brain.

In consideration of high intracranial activity and 63.5% PFS rate and not reached mPFS after 36.7 months follow-up in the CROWN trial,²² ALK-positive NSCLC patients shall benefit most using lorlatinib in the first-line treatment in the clinical practice. Nevertheless, only 10 ALK+ NSCLC patients were randomized to the lorlatinib group in China mainland, and published data of clinical trials regarding first-line treatment of lorlatinib is still limited to CROWN trail. There is a vast vacancy of efficacy and safety regarding first-line lorlatinib treatment in China ALK-positive NSCLC patients. Further,

first-line resistance mechanism of lorlatinib is still ambiguous,²³ the sequencing therapy after PD of first-line lorlatinib is far from definite, and how lorlatinib benefiting ALK-positive NSCLC patients in clinical practice beyond CROWN criteria should be further explored. There is no clear answer so far to these clinically relevant questions.

In addition, recent clinical studies have shown that continuation of TKI treatment beyond progression in patients with oligometastasis NSCLC can be an effective strategy to target tumor cells that still addicted to the EGFR pathway and prevent the disease flare observed after discontinuation of the targeted agent.^{24,25} Further more, for patients with oligometastases (means target lesions with residual disease, definition a maximum of 3 organs, and no more than 5 lesions in total), treatment should be considered in combination with local therapeutic approaches, such as surgery, local ablation or radiotherapy, to improve disease control and thereby long-term survival outcomes.²⁶ However, no studies have yet reported whether patients with ALK+ NSCLC can also benefit from the above treatment mode.

This real-word study is designed to prospectively explore whether local treatment (surgery, ablation, radiotherapy and others) can prolong the time to treatment discontinuation during 1L lorlatinib treatment in Chinese patients with unresectable ALK⁺ NSCLC. Since this is a non-interventional study (NIS) to observe the routine practice, there will not be any study required clinical interventions or laboratory assessments. Participation in this study is not intended to change the routine treatment received as determined by their attending physicians. Patients will be treated according to the routine medical practice in terms of visit frequency and types of assessments performed.

This study will enroll patients with ALK-positive non-small cell lung cancer locally diagnosed in about 6 sites in China from study setup to about Oct 2025, as the target observation population. Patients' effectiveness and safety data of first line treatment with lorlatinib will be collected after their first dose until the 60th month or patient death, loss to follow-up, or withdrawal from the study for any reason. The visit schedule

during study is not mandatory and follow local routine clinical practice.

The study data will be generated from the attending physician's routine clinical assessment during standard care. The data source used for data collection will be from electronic medical records/medical records or medical charts or other approved data source.

The database lock date is about Oct 2030 or the date of the death of the last enrolled patient.

2. STUDY OBJECTIVES

2.1. Objectives

Primary Objective:

- To evaluate the time-to treatment discontinuation (TTD) of lorlatinib with locally therapy in unresectable ALK-positive NSCLC patients who have received 1L lorlatinib in real-world settings;

Secondary Objectives:

- To evaluate the rwORR, rwDCR and real-world intracranial ORR, intracranial time to progression (IC-TTP) and TTP of 1L lorlatinib in real world setting ;
 - To explore the progression pattern in this therapeutic changing mode;
- To evaluate 1/2/3/4/5-year overall survival (OS) rate and OS of in each treatment cohort;
- To explore the association between the effectiveness of lorlatinib in first line for Chinese patients with ALK-positive locally advanced or metastatic NSCLC patients with baseline brain metastases (Yes or No) , ALK Fusion Variants ([V1, V2, V3] and

TP53 mutation status [TP53 mutation, TP53 WT]) if data is available in medical records;

- To evaluate the safety and tolerability of the therapeutic changing mode;
 - To explore the adverse events (AEs), the dose modification and the reason for interruption or discontinuation of lorlatinib in first line for Chinese ALK-positive locally advanced or metastatic NSCLC recorded in medical records;
 - To evaluate patient-reported outcomes (PROs) of health-related quality of life for this therapeutic mode;
 - To describe the demographic, clinicopathological and baseline co-mutation characteristics of enrolled patients.

Exploratory Objectives:

- To explore dynamic ctDNA change during lorlatinib treatment;
- To evaluate candidate biomarkers of sensitivity or resistance to lorlatinib in no-prior ALK-TKIs treatment tumor tissue and peripheral blood if available in real world setting;

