3.1 Study design

This is a prospective, observational, multi-center, parallel-group, real world study to explore therapeutic changing mode of locally therapy after 1L lorlatinib treatment in unresectable ALK-positive Non-Small Cell Lung Cancer (NSCLC). Patients with unresectable NSCLC must have no previous systemic treatment for advanced (Stage IIIB/C not amenable for multimodality treatment) or metastatic (Stage IV) disease. All subjects must have tumors that test, positive for ALK rearrangement, with methods of Ventana ALK (D5F3), fluorescence in situ hybridization (FISH), polymerase chain reaction (PCR), or next generation sequencing (NGS), or circulating tumor DNA (ctDNA) for ALK rearrangement, with method of NGS. All tumors will be of histo- and/or cytopathology consistent with NSCLC, (e.g., adenocarcinoma, Squamous-cell carcinoma, or mixed), or its pathologically accepted variants.

The study will collect and analyze effectiveness, safety, PRO of lorlatinib in first-line from approximately 100 ALK positive locally advanced or metastatic NSCLC patients from study beginning to last subject last visit across approximately 8 sites in the real-world setting in China.

Lorlatinib will be administered orally QD at approximately the same time of the day on a continuous daily dosing schedule, ie, without a break in dosing in the absence of drug-related toxicity. Patients must swallow the study medication whole and must not manipulate or chew the medication prior to swallowing. A dosing card will be provided to the patients to provide guidance for the correct use of lorlatinib. Patients must be instructed that should they miss a dose or vomit any time after taking a dose, they must not “make it up” with an extra dose. Instead, resume the subsequent doses as originally prescribed. Any missed dose may be taken up to 6 hours prior to the next scheduled dose, otherwise it should be skipped and dosing resumed with subsequent doses as prescribed. The patient must be instructed to record all doses (including missed or vomited) in a dosing diary supplied by the site. If doses are missed or vomited, this must be indicated in the source documents and Case Record Forms (CRFs).

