After lorlatinib treatment for 4 weeks, patients will receive an imaging assess. The patients who achieve PR or SD with oligometastasis (refer to target lesions with residual disease, a maximum of 3 organs, and no more than 5 lesions in total) should continue lorlatinib treatment and will receive imaging assess per 8-12 weeks. If target lesions indicate stable in 2 consecutive imaging, investigators will organize MDT and comprehensively evaluate patients' will to decide and choose local therapy. The local therapy includes surgery, ablation and, radiotherapy et al. After local therapy, patients should continue taking lorlatinib. While those who achieve CR or with multiple metastasis will continue lorlatinib treatment without any local therapy.

To dynamically monitor ctDNA changes in ALK + NSCLC patients during Lorlatinib treatment; to explore the correlation between ctDNA and Lorlatinib treatment efficacy .Patients need check the ctDNA-seq (10000x) in plamsa with NGS at baseline,4weeks after lorlatinib treatment and at disease progression.

Subjects will be on lorlatinib therapy until disease progression or unacceptable toxicity, new systemic anticancer therapy instituted, withdrawal of consent, death, or investigator decision dictated by protocol compliance, whichever occurs first.

Patients received continuous daily PO dosing of lorlatinib 100mg QD with/without locally therapy, from the date of first dosing (per the current protocol) or until one of the following criteria were met (whichever occurred first): disease progression; initiation of a new anti-cancer therapy; unacceptable toxicities; global deterioration of health-related symptoms; pregnancy; withdrawal of consent; loss to follow-up; death; investigator decision dictated by protocol non-compliance; or study termination. Patients who have progressive disease (PD) (per RECIST v1.1, by investigator review) and for whom the investigator believes it is in their best interest to continue lorlatinib treatment are allowed to continue lorlatinib therapy, at the discretion of the investigator, until any alternate or additional systemic anti-cancer therapy regimen was implemented.

At the time of progression and termination of study treatment, the patients could receive

any therapy at the judgment of the investigator. This study will take 1 years to enroll subjects, and each subject will be followed up for survival status and subsequent cancer therapies up to 60 months from the date of first dosing.

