9.2.2 Definition of Primary Endpoint

Time-to treatment discontinuation (TTD) is defined as the time from start of treatment to the date of discontinuation of lorlatinib.

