9.2.4 Definitions of Secondary Efficacy Endpoints

Real world Intracranial Objective Response Rate is defined as the proportion of subjects with a BOR of either CR or PR of intracranial disease, where BOR is the best response recorded from the start of treatment until disease progression or start of other anticancer therapy in real world setting. As per RECIST v1.1 guidelines, PR and CR do not need to be confirmed following initial response documentation.

Real world Objective Response Rate is defined as the proportion of subjects with a BOR of either CR or PR, where BOR is the best response recorded from the start of treatment until disease progression or start of other anticancer therapy in real world setting. As per RECIST v1.1 guidelines, PR and CR do not need to be confirmed following initial response documentation.

Real world Disease control rate is defined as the proportion of patients with complete response (CR) or partial response (PR) or subjects with stable disease (SD) as per investigator assessment according to RECIST 1.1 criteria in real world setting.

Overall Survival is defined as the time from start of treatment to the date of death for any cause. In the absence of confirmation of death, survival time will be censored at the last date the subject is known to be alive.

Real world Intracranial Time To Progression is defined as the time from randomization to the date of the first documentation of objective progression of intracranial disease, based on either new brain metastases or progression of existing brain metastases in real world setting.

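### Survival and time to treatment discontinuation by treatment cohort are counted from the first lorlatinib dose, but the local-therapy group forms months later by response and stability, so the by-cohort results cannot be read as an effect of local therapy and probably favour it

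*Protocol*

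**What the plan says.** Section 2.1 lists as a secondary objective: "To evaluate 1/2/3/4/5-year overall survival (OS) rate and OS of in each treatment cohort". Section 9.2.4 fixes the clock: "Overall Survival is defined as the time from start of treatment to the date of death for any cause". The primary endpoint has the same origin. Section 9.2.2 says TTD "is defined as the time from start of treatment to the date of discontinuation of lorlatinib".

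The treatment groups form later, under Section 3.1. First, "After lorlatinib treatment for 4 weeks, patients will receive an imaging assess". Patients with partial response (PR) or stable disease (SD) and oligometastasis "should continue lorlatinib treatment and will receive imaging assess per 8-12 weeks". Then: "If target lesions indicate stable in 2 consecutive imaging, investigators will organize MDT", and the multidisciplinary team (MDT) and the patient decide on local therapy. For the others: "While those who achieve CR or with multiple metastasis will continue lorlatinib treatment without any local therapy".

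The protocol does not say what the treatment cohorts are. Section 3.1 labels the study as follows: "This is a prospective, observational, multi-center, parallel-group, real world study". The only treatment split in its text is lorlatinib with or without local therapy.

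On purpose, the Introduction asks whether local treatment can prolong TTD, and Section 9.1 words the primary objective as showing that it does. Section 9.1 also calls the study descriptive, with no specified hypothesis. Section 9.2.5 plans Kaplan-Meier summaries for OS, with log-rank tests for subgroups. The subgroups it names are baseline factors.

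**The concern.** A patient who follows the stated pathway to local therapy must first be alive, progression-free and stable on two scans. Counted from first dose, that waiting time is event-free by construction (immortal time). Patients who progress, stop lorlatinib or die during it fall by default into the group without local therapy. They are joined there by complete responders (CR) and patients with multiple metastases, whom Section 3.1 keeps on lorlatinib alone.

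The two groups would therefore differ in OS and TTD even if local therapy did nothing. The discussion of bias in Section 10.2 covers the choice of sites, loss to follow-up and missing data, but not how these groups form. At stake is the study's central question, whether adding local therapy helps.

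**Working it through.** **No stated figure to reproduce.** Section 9.1 gives about 100 patients and says this number does not come from statistical assumptions.

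**Step 1: when the groups form.** Scans are at week 4, then every 8-12 weeks (Section 3.1).
- If the week-4 scan counts as the first of the two stable scans, the second falls at 4 + 8 = week 12 to 4 + 12 = week 16.
- If it does not count, the second falls at 4 + 16 = week 20 to 4 + 24 = week 28.

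These weeks are nominal. Section 7.2.1 puts the first post-baseline scan at 8 weeks and later scans every cycle, and Section 3.1 also says there is no fixed visit schedule. These passages must be reconciled.

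**Step 2: who is already out by then.** The Introduction cites 12-month progression-free survival of 78% on first-line lorlatinib. With a constant hazard over the first year, the share progressed or dead by week w is 1 − 0.78^(w/52):

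| Week | Progressed or dead |
|---|---|
| 12 | 5.6% |
| 16 | 7.4% |
| 20 | 9.1% |
| 28 | 12.5% |

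None of these patients can enter the local-therapy group through the stated pathway.

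**Step 3: size of the distortion when local therapy has no effect.** Simulation inputs from the Introduction: progression-free survival of 78%, 68.2% and 63.5% at 12, 24 and 36 months, used as a proxy for TTD, with the last interval's hazard carried to month 60. Assumed, because the documents do not give them:
- 40-50% of patients are oligometastatic with PR or SD, and 5-30% have CR;
- 70% of patients who meet the criteria receive local therapy;
- median survival after discontinuation is 18 months.

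Hazard ratios, local therapy versus none, counted from first dose, with equal prognosis in all response groups:

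| Decision point | OS | TTD |
|---|---|---|
| Week 12 | 0.83 | 0.84 |
| Week 20 | 0.72 | 0.73-0.74 |
| Week 28 | 0.62-0.63 | 0.65-0.66 |

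At week 28, 60-month OS is about 75% with local therapy and 63-64% without. Changing the post-discontinuation median to 9 or 36 months gives OS hazard ratios of 0.81-0.83 at week 12 and 0.62-0.63 at week 28.

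**Step 4: sensitivity to the response mix.**
- CR at hazard 0.5 and multiple metastases at hazard 1.5, relative to the oligometastatic group: OS hazard ratio 0.50 to 0.88.
- 30% CR at hazard 0.3 and no penalty for multiple metastases: 1.16 at week 12, 1.01 at week 20 and 0.90 at week 28.

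**Step 5: does the remedy work?** In the same null scenarios, the analysis was restricted to patients who met the criteria and were still on lorlatinib at the decision point. Hazard ratios were then 0.97-1.03 for OS and 0.98-1.03 for TTD. This assumes that uptake is unrelated to prognosis.

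**Step 6: size of the proper comparator.** Per 100 patients, (40 to 50) × (1 − 0.70) = 12 to 15 meet the criteria but are not treated. Multiplying by the share still on lorlatinib, 12 × 0.875 = 10.5 and 15 × 0.944 = 14.2, so about 10 to 15. This is before the dropout of at least 20% given in Section 9.1.

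**The case against.** The strongest reply is that no OS comparison between cohorts is planned. Section 9.2.5 gives Kaplan-Meier summaries, its named subgroups do not include local therapy, and Section 10.2 says that no hypotheses will be tested. This stands as far as it goes: there is no formal OS test to invalidate. It does not remove the problem, because five years of OS reported by cohort show the same bias side by side. For TTD, the comparative aim is written into the Introduction and Section 9.1.

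Second, the cohorts are undefined and the design figure is not available in the text reviewed, so a two-group split is an inference. That also stands. It is a reason to define them.

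Third, Section 6.2.4 permits local therapy after two stable scans without repeating the response and oligometastasis condition. It would therefore be too strong to say that nobody outside that condition could receive it.

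Fourth, the statistical analysis plan, which is not shown, may add a landmark or time-dependent analysis. It may, but the protocol already fixes both the time origin and the by-cohort reporting.

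A reader might infer that local therapy is bound to look beneficial. The documents do not support that. Complete responders sit in the group without local therapy, and one null scenario gives a hazard ratio of 1.16.

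**Conclusion.** The concern holds in this form: OS or TTD by treatment cohort, counted from first dose, is not interpretable as an effect of local therapy and is probably biased in its favour. The structural part rests on the protocol's own text: the time origin, the two-scan condition, and early failures falling by default into the other group.

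The size is illustrative. With equal prognosis across response groups, null OS hazard ratios are about 0.62 to 0.83. Uptake, response mix and survival after discontinuation are assumptions, and a large complete-responder share with a good prognosis could cancel or reverse the direction. TTD matters most, because it is the primary endpoint and carries the comparative aim. OS from first dose for the whole population is sound and needs no change.

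**What to change.** In Sections 2.1 and 9.2:
- Define the treatment cohorts.
- Keep OS and TTD from first dose for the whole population.
- For any result by local therapy, TTD first and then OS, treat local therapy as a time-dependent exposure. Alternatively, use a landmark at a prespecified time after the second qualifying scan, with groups set by treatment received by then. The window matters: starting the clock at the scan and grouping by later treatment leaves immortal time between scan and delivery.
- Restrict this comparison to patients who met the same criteria and are still on lorlatinib.
- Report complete responders, patients with multiple metastases and early progressors as separate descriptive groups.
- State that confounding by MDT and patient choice remains and that the comparison is exploratory.

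Record three items: the date the criteria were met, the date of local therapy, and the reason it was not given. Reconcile the scan schedules in Sections 3.1 and 7.2.1, since they set the landmark.

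The cost is wording and three data fields, with no extra patients or visits and no change to care. The downside is a small comparator, about 10 to 15 of 100 patients under the assumed shares, and probably a less favourable apparent benefit.
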